3.2 Exclusion Criteria

Patients who meet any of these criteria are not eligible for enrollment as study participants

- Prematurity: < 37 weeks post gestational age at time of surgery
- Treatment with intravenous steroids within the two days prior to scheduled surgery.
- Participation in research studies involving the evaluation of investigational drugs or vaccines within 30 days of randomization.
- Suspected infection that would contraindicate steroid use (e.g. – Herpes)
- Known hypersensitivity to IVMP or one of its components or other contraindication to steroid therapy (e.g. - gastrointestinal bleeding).
- Preoperative use of mechanical circulatory support or active resuscitation at the time of proposed randomization.
- Inability to comply with study procedures.

4 Study Design

This is a multi-center, prospective, randomized, double blind, placebo controlled study of intraoperative MP in neonates undergoing CPB. Patients will be allocated to one of the 2 study groups in the ratio of 1:1. The randomization will be stratified by corrective vs. palliative surgery and by surgeon. The Primary Endpoint is a composite morbidity-mortality outcome, evaluated as intention to treat (ITT). Secondary endpoints include inotropic score, incidence of LCOS, fluid balance, ICU stay parameters, levels of inflammatory markers, safety parameters, and neurodevelopmental outcomes at 1 year. A two-sided test with a type I error rate of 0.05 will be used for all endpoints with no adjustments of the p-value for multiple testing.

It is expected that 190 patients (95 patients per treatment arm) will be needed to be enrolled in the study to show a significant difference between groups. The annual amount of eligible & consenting patients at MUSC for this trial and a similar trial over 3 years was 35 cases/year. The annual amount of eligible patients at Children's Healthcare of Atlanta based on the surgical volume in 2012 would be 74 neonates. Anticipating a 70% consent rate would result in 50 cases a year. As such, this study would expect to reach the goal of 190 evaluable subjects in 4 years, within the 5 year proposed grant cycle.

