12.2 Sample Size and Power Calculation for Secondary Endpoints

From the wide variety of Secondary Endpoints, a subset have available data to statistically assess whether or not they are adequately powered from the enrollment necessary to power the Primary Endpoint.

- ICU Length of Stay (LOS). Preliminary data suggest that ICU LOS data are highly skewed in this population, with 20% having ICU LOS > 10 days. We performed statistical simulations (with 5,000 replications) in which we assumed that 40% of subjects receiving placebo would have ICU LOS > 10 days but similar distribution within the ≤10 day and >10 day categories, and under such assumptions we found that having 95 subjects per group provided about 75% power to detect a difference of this magnitude.
- Maximum Inotropic Score Over 36 Hours. Graham⁵ found maximum inotropic scores over the first 36 hours postoperatively of 14.4 ± 3.6 vs. 15.0 ± 3.9 for intraoperative MP alone vs. combined preoperative and operative MP. Assuming similar standard deviations in this study, 95 patients per arm with analyzable data will provide >95% power to detect a difference of ≥ 2 between groups.
- Neurodevelopmental Outcomes. The Pediatric Heart Network Single Ventricle Reconstruction Trial⁴⁷, evaluated neurodevelopmental outcomes at 12 months of age using the Bayley Scales of Infant Development. Their results revealed a mental scale raw score of 91.93 with a standard deviation of 7.25 in 172 infants undergoing staged palliation for hypoplastic left heart syndrome and related variants. Although dropout is unlikely prior to assessing the primary endpoint, it is more likely prior to the 12 month follow-up. Assuming a similar standard deviation and a 15% dropout rate, 81 patients per arm with analyzable data will provide 99% power to detect a difference of 5 points.

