12.4 Statistical Methods

Descriptive statistics will be used to characterize the two treatment groups with respect to demographics and baseline clinical characteristics. T-tests, chi-square tests, and non-parametric statistical tests will be used, as appropriate, to compare the groups at baseline. Any significant imbalances will be accounted for in the analyses using multivariable techniques. The primary intention-to-treat analysis comparing the composite outcome between treatment groups will be conducted using generalized linear model. The primary analysis will be adjusted for underlying diagnosis and surgeon. Logistic regression models will be used for the per-protocol analysis and for analyses of secondary categorical outcomes. For continuous variables such as change from baseline in vital signs, hematology, and clinical chemistry parameters, analysis of covariance (ANCOVA) will be utilized with the baseline value used as covariates. Unless otherwise stated, baseline is defined as the last observation before the administration of the study drug. Time to event data (duration of mechanical ventilation, length of ICU stay, and length of hospitalization) will be assessed via non-parametric log-rank tests.

Once half of the study subjects have been recruited and assessed, an interim analysis will also be conducted and presented to the DSMC, for which the p-value thresholds for stopping the study for superiority or futility will be 0.003 and 0.72, respectively. The p-value used at the end of the study with full enrollment will be 0.049, preserving an experiment-wise 2-sided alpha level of 0.05. These stopping thresholds are based on an O'Brien-Fleming alpha spending function. All analyses will be conducted in SAS v9.2 (Cary, NC).

Multiple correlation analyses will be performed between the inflammatory markers and other continuous outcome measures, such as fluid balance, inotropic score and hemodynamic variables. An assessment will also be made of the association between the inflammatory markers and categorical variables, such as the composite morbidity-mortality outcome and its components. Analyzed safety variables will include all reported adverse events, the incidence of acute renal injury and postoperative creatinine, hyperglycemia and infection. All patients who are randomized, received study drug, and underwent cardiopulmonary bypass will be included in the safety analyses.

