Duration mechanical ventilation (hours), ICU stay (hours), and hospitalization (days) Fluid intake (ml) and urine output (ml). In addition the number of days alive and out of the hospital at 90 days post cardiac surgery will be recorded.

- Bayley Scales of Infant Development

The Bayley Scales of Infant Development (BSID-III is the current version) is a standard series of measurements used primarily to assess the motor (fine and gross), language (receptive and expressive), and cognitive development of infants and toddlers, ages 0-3. This measure consists of a series of developmental play tasks and takes between 45 - 60 minutes to administer. Raw scores of successfully completed items are converted to scale scores and to composite scores. These scores are used to determine the child's performance compared with norms taken from typically developing children of their age. This will be performed in conjunction with an evaluation from a specialist in Developmental Pediatrics at 12 months of age.

The results of this evaluation will be made available to the parent(s)/LAR and pediatrician. Appropriate consultation with occupational, physical or speech therapist or follow up with Developmental Pediatrics will be made based on the specialist recommendations.

- Hemodynamics and Post-operative Course

During the operative period, hemodynamic values will be recorded at time intervals coinciding with the blood collection. All measurements will be obtained from the catheters and monitors in place for the normal clinical conduct of the surgical procedure. In the postoperative period, the requirement for inotropic medications, duration of intubation and mechanical ventilation, duration of ICU and hospital stay, and fluid status will be documented from existing medical documentation. Any data obtained through the course of the study may be used for clinical management of the patient. Data related to the level of circulating biomarkers will be collected but run in batch at a core laboratory, therefore this will not be immediately available for direct patient care. All historical and demographic data will come from existing records.

- Quantitative Measures of Inflammatory Biomarkers

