12.6 Study Data Collection

12.6.1 Table 2: Schedule of Measurements

	(a)PREOP	(c)T=1, 2 OR	PCICU	T=3 4 hrs ± 1 hr	8 hrs ± 1 hr	T=4 12 hr ± 1 hr	T=5 24 hr ± 1 hr	36 hr ± 1 hr	D/C	30 days Post- op	90 days Post- op	1 Year Followup 12-14 Months
Windows			Arrival									
Informed Consent	X											
Inclusion/Exclusion	X											
Demographics	X											
Diagnosis Details		X										
Med/Surg History	X							X				
Randomization	X											
Vital Signs	X		X	X	X	X	X	X				
ABG, Ion Ca ⁺⁺ , Lactate (e)	X		X	X	X	X	X	X				
Hematology (e)	X		X				X	X				
Biochemistry (e)	X		X				X	X				
Diuretics								X				
Biomarker		(b)XX		X		X	X					
Urine Sample		X	X				X					
Cardio-Pulmonary Bypass (CPB)		X										
Daily Inotropic Scores	X		X	X	X	X	X	X				
Highest Inotropic Score								X				
36 HR Assessment								X				
I/O (d)						X		X				
LCOS								X				
Duration of Ventilation									X			
Length of ICU & Hospital Stay									X			
Composite Outcome									X	X		
Days alive & out of hospital											X	
Bayley Scale												X
Study Completion												X
Adverse Events	X	X	X	X	X	X	X	X	X			X

- (a) Last Values before Surgery
- (b) 2 Biomarker Samples in OR regardless of time
- (c) T= Time point of blood/urine sample for study
- (d) I/O collected 1 day post-op
- (e) These laboratory values are standard of care and will be recorded at these time points if obtained. They are not required

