12.8 Sample Size and Power Calculation for Secondary Endpoints

From the wide variety of Secondary Endpoints, a subset have available data to statistically assess whether or not they are adequately powered from the enrollment necessary to power the Primary Endpoint.

- ICU Length of Stay (LOS). Preliminary data suggest that ICU LOS data are highly skewed in this population, with 20% having ICU LOS > 10 days. We performed statistical simulations (with 5,000 replications) in which we assumed that 40% of subjects receiving placebo would have ICU LOS > 10 days but similar distribution within the ≤10 day and >10 day categories, and under such assumptions we found that having 95 subjects per group provided about 75% power to detect a difference of this magnitude.
- Maximum Inotropic Score Over 36 Hours. Graham⁵ found maximum inotropic scores over the first 36 hours postoperatively of 14.4 ± 3.6 vs. 15.0 ± 3.9 for intraoperative MP alone vs. combined preoperative and operative MP. Assuming similar standard deviations in this study, 95 patients per arm with analyzable data will provide >95% power to detect a difference of ≥ 2 between groups.
- Neurodevelopmental Outcomes. The Pediatric Heart Network Single Ventricle Reconstruction Trial⁴⁷, evaluated neurodevelopmental outcomes at 12 months of age using

the Bayley Scales of Infant Development. Their results revealed a mental scale raw score of 91.93 with a standard deviation of 7.25 in 172 infants undergoing staged palliation for hypoplastic left heart syndrome and related variants. Although dropout is unlikely prior to assessing the primary endpoint, it is more likely prior to the 12 month follow-up. Assuming a similar standard deviation and a 15% dropout rate, 81 patients per arm with analyzable data will provide 99% power to detect a difference of 5 points.

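### The ICU-stay power of about 75% names no test; the planned log-rank test has about 68% under the stated assumptions with all stays observed

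*Combined protocol and SAP*

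**What the plan says.** Section 12.2, repeated in 12.8, gives the basis for the ICU-stay power. The starting point is: "Preliminary data suggest that ICU LOS data are highly skewed in this population, with 20% having ICU LOS > 10 days". For the simulation of 5,000 replications, "we assumed that 40% of subjects receiving placebo would have ICU LOS > 10 days", with similar distributions within the short-stay and long-stay categories. The result is that "under such assumptions we found that having 95 subjects per group provided about 75% power to detect a difference of this magnitude". The text does not give the test, the shape of the distribution within each category, or any censoring.

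The analysis is fixed elsewhere. Section 12.4, repeated in 12.10, states: "Time to event data (duration of mechanical ventilation, length of ICU stay, and length of hospitalization) will be assessed via non-parametric log-rank tests". Section 4 adds: "A two-sided test with a type I error rate of 0.05 will be used for all endpoints". Section 12.5.2 records ICU stay in hours, and Table 2 in section 12.6.1 collects it at discharge. No follow-up cut-off for ICU stay appears anywhere.

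**The concern.** A power figure can be interpreted only for a named test. The one test the plan assigns to ICU stay is the log-rank test, so a reader will take 75% as its power.

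The assumed scenario does not suit that test. The arms differ only in the share leaving by day 10, and beyond day 10 the remaining stays follow the same distribution in both arms. Discharges after day 10 therefore add variance to the log-rank statistic but no signal. This suggested that 75% was too high.

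Section 12.2 is there to show which secondary endpoints are adequately powered at the enrolment set by the primary endpoint. If its figure is too high for the planned test, a null ICU-stay result would be read as stronger evidence than it is.

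**Working it through.** **Inputs**
- 95 per arm; share staying beyond 10 days 40% on placebo and 20% on MP (12.2, 12.8). The 20% is stated for preliminary data. It is the only other rate given, so it is read as the MP rate.
- Within-category distributions: described as similar, taken here as identical.
- Log-rank test (12.4, 12.10), two-sided 0.05 (section 4).
- All stays observed and no deaths, since the plan states no cut-off or death rule.

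**The plan's own figure.** It cannot be reproduced directly, because the test is not named. The check is therefore the power of the planned test.

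**Approximation by hand.** With identical within-category distributions and continuous, fully observed times, the log-rank test depends only on ranks, so the undisclosed shape drops out. Let u run from 0 to 1 through the category of 10 days or less. The shares still in the ICU are S_P = 1 − 0.6u (placebo) and S_M = 1 − 0.8u (MP).

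- Expected observed-minus-expected discharges on MP = 95 × ∫ (0.8·S_P − 0.6·S_M)/(S_P + S_M) du. The numerator is 0.8 − 0.48u − 0.6 + 0.48u = 0.2. The result is 95 × 0.2 × ln(2/0.6)/1.4 = 16.34. Beyond day 10 the contribution is zero.
- Variance up to day 10 = 95 × 1.4 × ∫ S_P·S_M/(S_P + S_M)² du = 95 × 1.4 × 0.2454 = 32.64.
- Variance beyond day 10 = 95 × 0.6 × (0.4 × 0.2/0.6²) = 12.67.
- Standardised effect = 16.34/√(32.64 + 12.67) = 16.34/6.73 = 2.43.
- Power ≈ Φ(2.43 − 1.96) = Φ(0.47) = **68%**.

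Stopping at day 10 would remove the second variance term: 16.34/√32.64 = 2.86, and Φ(0.90) = 82%. Simulation with that cut-off gives about 81%.

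**Simulation of the planned test**

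| Setting | Log-rank power |
|---|---|
| Stays in whole hours, lognormal mixture matched to the protocol's Table 1, 20,000 replicates | 68.2% (SE 0.33) |
| Continuous times, rank-only, 60,000 replicates | 68.4% (SE 0.2) |
| All other shapes and tie patterns tried | about 66% to 70% |
| Equal arms (null check) | 4.9% to 5.4% rejections |

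At 5,000 replications the Monte Carlo standard error at 75% is √(0.75 × 0.25/5,000) = 0.6 points. A gap of about 7 points is roughly 11 standard errors, so simulation noise does not explain it.

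**What would give 75% with the log-rank test**
- Sample size: 95 × [(1.960 + 0.674)/2.427]² ≈ 112 per arm by the approximation. By simulation, 105 per arm gives about 73% and 110 per arm about 75%.
- Effect: a placebo share of 41.5% gives 73.4%, and 42% gives 75.5%.
- A cut-off, depending on the assumed shape: 74% to 81% at day 14, 70% to 79% at day 21, 69% to 76% at day 30, and 68% to 70% at day 60 or later. The day-21 and day-30 ranges are sensitive to shape: another set of shapes gave 69% to 71% at day 30.

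**Other tests, same scenario**
- Wilcoxon rank-sum: 66% to 68%, and 70.5% with very coarse ties.
- t-test on log stay: 55% to 75%, depending on shape.
- t-test on raw stay: 57% to 75%, depending on shape.
- One-sided 0.05 log-rank: 76% to 79%, but section 4 excludes one-sided testing.
- Chi-square on the share beyond 10 days: (0.20 − 1.96 × √(2 × 0.3 × 0.7/95))/√((0.24 + 0.16)/95) = (0.20 − 0.130)/0.0649 = 1.07, which gives 86%.

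**The case against.** The strongest reply is that the plan never says the log-rank test was what it simulated. The 75% may be correct for a log-rank test with a cut-off, or for a t-test under a suitable shape; what is shown is that the figure cannot be tied to the planned test, not that someone miscalculated. That is fair, and the 68% is conditional for that reason. It does not rescue the text: if another analysis was simulated, 12.2 and 12.8 describe one analysis and 12.4 and 12.10 another, and one pair has to change.

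A second reply is that the inputs are loose. The plan says similar rather than identical distributions, says about 75%, and does not label 20% as the MP rate. A placebo share of 42% would close the gap. This also stands in part, but the stated placebo figure is 40%, and no other rate is available for a difference of the size described.

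A third reply is that little depends on it. Both 75% and 68% fall below the 80% used for the primary endpoint, the sample size is set by the composite, and a null result should be read from its estimate and confidence interval. This stands, and it limits the weight of the point.

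Deaths are a separate matter. The plan does not say how in-hospital deaths enter the three duration analyses, and the 68% assumes none. At assumed mortalities of 2%, 5% and 10%, equal in both arms, treating deaths as never discharged lowers log-rank power to about 56%, 44% and 31%. Censoring at death, independently of stay length, leaves 64% to 68%. These figures depend on an assumed convention and rate, and the conclusion here does not rest on them.

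**Conclusion.** The stated power does not hold for the test the plan specifies. A two-sided 0.05 log-rank test with 95 per arm and 20% against 40% staying beyond 10 days has about 68% power, roughly 7 points below the printed figure.

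This rests on four readings: 20% is the MP rate, the within-category distributions are identical, every stay is observed to its end, and there are no deaths. Within those readings the undisclosed shape matters little. The correction is worth making, but it does not touch the primary endpoint or the enrolment target, and death is also captured by the composite and by days alive and out of hospital.

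**What to change.** In 12.2 and 12.8, name the test and restate the ICU-stay power as about 68% for the two-sided 0.05 log-rank test, with all stays observed to their end and no deaths. State that 20% is the assumed MP rate and give the within-category distribution used.

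If a cut-off or a different test was simulated, state it there and bring 12.4 and 12.10 into line, so that the power and the analysis refer to the same procedure.

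While those sections are open, a sentence in 12.4 and 12.10 on how in-hospital deaths enter the duration analyses would help. If deaths are ranked worst, or discharge alive is analysed, that power needs its own calculation, because the 68% does not apply to it.

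The cost is wording in four sections and a rerun of the existing simulation. The printed power becomes less favourable. No new data are needed and the total of 190 does not change.

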12.3 Subgroup Analyses

The modified ITT population, defined as the set of all patients randomized to treatment and underwent cardiopulmonary bypass, will be analyzed and presented for the Primary Endpoint. The same analyses will be conducted on the PP population, defined as those patients who are randomized, receive study drug as defined in the protocol, and have no major protocol violations preventing analysis (e.g. – post-op patients who receive steroids off-protocol). A two-sided test

with alpha of 0.05 will be used. The following subgroups will be analyzed for the Primary Endpoint:

Underlying diagnosis:	Palliated vs. Corrective procedure
Age:	≤ 7 days vs. >7 days
Body weight:	≤ 2.5 kg vs. >2.5 kg

12.4 Statistical Methods

Descriptive statistics will be used to characterize the two treatment groups with respect to demographics and baseline clinical characteristics. T-tests, chi-square tests, and non-parametric statistical tests will be used, as appropriate, to compare the groups at baseline. Any significant imbalances will be accounted for in the analyses using multivariable techniques. The primary intention-to-treat analysis comparing the composite outcome between treatment groups will be conducted using generalized linear model. The primary analysis will be adjusted for underlying diagnosis and surgeon. Logistic regression models will be used for the per-protocol analysis and for analyses of secondary categorical outcomes. For continuous variables such as change from baseline in vital signs, hematology, and clinical chemistry parameters, analysis of covariance (ANCOVA) will be utilized with the baseline value used as covariates. Unless otherwise stated, baseline is defined as the last observation before the administration of the study drug. Time to event data (duration of mechanical ventilation, length of ICU stay, and length of hospitalization) will be assessed via non-parametric log-rank tests.

Once half of the study subjects have been recruited and assessed, an interim analysis will also be conducted and presented to the DSMC, for which the p-value thresholds for stopping the study for superiority or futility will be 0.003 and 0.72, respectively. The p-value used at the end of the study with full enrollment will be 0.049, preserving an experiment-wise 2-sided alpha level of 0.05. These stopping thresholds are based on an O'Brien-Fleming alpha spending function. All analyses will be conducted in SAS v9.2 (Cary, NC).

Multiple correlation analyses will be performed between the inflammatory markers and other continuous outcome measures, such as fluid balance, inotropic score and hemodynamic variables. An assessment will also be made of the association between the inflammatory markers and categorical variables, such as the composite morbidity-mortality outcome and its components. Analyzed safety variables will include all reported adverse events, the incidence of acute renal injury and postoperative creatinine, hyperglycemia and infection. All patients who are randomized, received study drug, and underwent cardiopulmonary bypass will be included in the safety analyses.

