7.1.3 Randomization

This is a randomized placebo-controlled multicenter study of intraoperative MP in neonates undergoing CPB. The goal for subject randomization for this trial is to prevent potential selection biases, prevent serious imbalances in the distributions of important baseline prognostic factors and ensure the compatibility of the two subject groups. Based on knowledge from previous studies and clinical experiences, cardiac operation (corrective vs. palliative surgery) and surgeon are potential prognostic factors that may affect the primary outcome. Serious imbalances in the distribution of either of these two factors may reduce the compatibility of the study groups, and therefore affect the interpretation and the recipient of the trial results. Eligible subjects are randomized at 1:1 ratio to either the intraoperative methylprednisolone (MP) or placebo treatment group. See section 11 for more details. Randomization should occur as close as possible to scheduled surgery but may occur at any time prior to surgery.

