12 STATISTICAL CONSIDERATIONS/ANALYTICAL PLAN

12.1 Sample Size and Power Calculation For Primary Endpoint

Using data from the previous steroid study performed by [name] the incidence of a similar composite endpoint occurred in 33% of the subjects. This proposed study is powered to detect an absolute difference of 20% between groups. Enrollment of 190 patients (95 per treatment group) will be required to provide 80% power to detect this difference between groups, with an experiment wise alpha of 0.05 (two-sided), allowing for 1 interim look at the data to assess for superiority and futility. The power analysis was performed using Cytel's East software package (Cambridge, MA) and assumes an O'Brien Fleming alpha spending function.

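### Baseline significance tests decide which extra covariates enter the analyses, so the primary model is not fixed in advance and may differ between the interim and final looks

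*Combined protocol and SAP*

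**What the plan says.** Section 12.4 (Statistical Methods) describes the baseline comparison: "T-tests, chi-square tests, and non-parametric statistical tests will be used, as appropriate, to compare the groups at baseline". The next sentence gives the consequence: "Any significant imbalances will be accounted for in the analyses using multivariable techniques". Section 12.10 repeats both sentences. Neither section lists the variables to be tested or the significance level that triggers adjustment, and neither limits the rule to secondary endpoints.

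The text then turns directly to the primary analysis, which "will be conducted using generalized linear model". It names two covariates: "The primary analysis will be adjusted for underlying diagnosis and surgeon". The subgroup list in 12.3 shows that underlying diagnosis means "Palliated vs. Corrective procedure". These two covariates match the stratification in section 4: "The randomization will be stratified by corrective vs. palliative surgery and by surgeon". They are also the only factors that section 7.1.3 (repeated in section 11) singles out: "cardiac operation (corrective vs. palliative surgery) and surgeon are potential prognostic factors that may affect the primary outcome".

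The interim analysis takes place at half enrolment, with p-value thresholds of 0.003 for superiority and 0.72 for futility. The final threshold is 0.049. Section 12.11 refers to a subsequent SAP, but the supplied text contains no further covariate list.

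**The concern.** The covariate set for the primary comparison consists of the two named factors plus whatever the baseline tests return. In a properly randomised trial, a significant baseline difference is a chance finding. Its p-value measures how unusual the imbalance is, not whether the variable predicts the composite outcome. The rule can therefore admit variables that do not matter and leave out variables that do.

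Two consequences follow. First, nobody can write down the primary model until the baseline data have been compared by arm. Second, the imbalances at half enrolment need not be those at full enrolment. The interim p-value and the final p-value may then come from different models, although the stopping thresholds are set for one test followed over time.

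**Working it through.** **1. The plan's own figures.** These reproduce, so the concern is about the model and not the design.
- Inputs from 12.1: 33% event rate, 20-point difference, 80% power, two-sided 0.05, 95 per arm. Taking 33% as the lower rate gives 53% vs 33%, with a mean of 43%.
- Formula: n per arm = [1.96·√(2·0.43·0.57) + 0.842·√(0.53·0.47 + 0.33·0.67)]² / 0.20² ≈ 95.0, which the program rounds up to 96. Power at 95 per arm is 80.0%.
- An O'Brien-Fleming-type spending function at half information gives 0.00305 at the interim and 0.0490 at the end, matching the stated 0.003 and 0.049.

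**2. Chance of at least one added covariate.** The trigger level is assumed to be 0.05, because the plan gives none. The number of variables k is also assumed. Table 2 and section 12.5.2 schedule five vital signs, six blood-gas items and thirteen biochemistry items before surgery (5 + 6 + 13 = 24), besides demographics, history and hematology, so k = 10 to 20 is plausible. For independent tests the chance is 1 − 0.95^k.

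**3. Chance that the selected set differs between looks.** For one variable, the standardised imbalances at half and full enrolment are correlated √0.5 = 0.71. From the bivariate normal distribution, the probability of significance at both looks is 0.0169. An imbalance that is significant at the interim therefore stays significant at the end with probability 0.0169/0.05 = 34%. The probability of significance at exactly one look is 2 × (0.05 − 0.0169) = 0.066. For k independent variables the chance of a different set is 1 − (1 − 0.066)^k.

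| k | At least one addition (final) | Different set at the two looks |
|---|---|---|
| 10 | 40% | 50% |
| 15 | 54% | 64% |
| 20 | 64% | 75% |

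Positive or negative correlation among the baseline variables would lower both columns.

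**4. Effect on power and type I error.** Logistic models were simulated with 190 infants at nominal 0.049. Two of the extra covariates were truly prognostic, with strengths that are assumptions. The settings differ in other details, so compare within rows only.

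| Extra covariates; assumed strength per SD | Power: named factors only | Power: trigger rule | Power: two prognostic covariates fixed in advance | Type I error: trigger rule |
|---|---|---|---|---|
| 10; odds ratio 1.5 each | 80.7% | 81.2% | 84.2% | 4.9% |
| 10; odds ratio 2.0 each | 80.6% | 80.9% | 86.6% | 4.4% |
| 15; log odds ratios 0.8 and 0.6 | 74.9% | 75.1% | 82.1% | 4.0% |
| 15; log odds ratios 0.4 and 0.3 | 79.4% | 79.1% | 81.9% | 5.0% |

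The rule moves power by half a point or less in either direction, which is within simulation error. With 10 extra covariates it picked up at least one of the two prognostic ones in only 9% to 10% of trials, which explains why it gains nothing. Fixing the prognostic covariates in advance gained about 2.5 to 7 points. If the covariates chosen are not prognostic, the gain is nil.

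**The case against.** Four points can be made for the plan.

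- **The named pair may be meant as the primary model.** On this reading, imbalance adjustment is supplementary. That is possible, but the sentence speaks of the analyses without restriction and stands immediately before the primary analysis. The text does not exclude it.
- **A later SAP may settle the matter.** It may, but the supplied text states a positive rule, and nothing in it withdraws that rule.
- **A reader might infer that precision from known prognostic factors is lost.** The document does not support this. The two factors it names as prognostic are in the primary model whatever the baseline tests show. Only precision from other variables could be forgone, and the document nowhere calls age or weight prognostic; they appear as subgroup factors.
- **A reader might infer that the rule inflates type I error.** Applied mechanically at one level, it does not: the simulated values are 4.0% to 5.0% against a nominal 4.9%. Only when the most favourable of three readings was picked each time (no trigger, trigger at 0.05, trigger at 0.10) did the error reach about 5.8%. Nothing in the document suggests that practice, although the unstated level leaves room for it.

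It is also fair to say that the number of tests, their level and their independence are assumptions, and that a triggered addition costs no power in itself. Those points limit the size of the concern. They do not supply a model that is fixed in advance.

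**Conclusion.** The concern holds in a limited form. As written, 12.4 and 12.10 let baseline p-values settle the covariate set of the primary analysis. The model is therefore not prespecified, and it may differ between the looks to which the 0.003, 0.72 and 0.049 thresholds apply. Under independence, a 0.05 trigger and 10 to 20 variables, an addition occurs in 40% to 64% of trials and the sets differ between looks in about 50% to 75%. With correlated variables these are upper figures.

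The harm is to prespecification and to the coherence of the two looks, not to the false-positive rate. The rule has no offsetting benefit, since it gains no power. The gain from naming further covariates instead lies between about 0 and 7 points and depends wholly on their prognostic strength, which the document does not give. This is a cheap improvement and not a fault that undermines the trial.

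**What to change.** - Delete the imbalance sentence from 12.4 and 12.10.
- State one primary model for both the interim and final analyses: treatment, surgery type and surgeon, plus any further already-collected covariates, with their functional form, named before unblinding. Age and body weight at surgery are candidates, because the planned subgroups already require them. Whether they add power depends on how prognostic they are.
- Present the baseline table descriptively, without p-values.
- If adjustment for observed imbalances is still wanted, keep it as a labelled sensitivity analysis.

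The cost is a wording change and, if both candidates are entered as single continuous terms, two extra model degrees of freedom. No new data are needed, and the sample size stays at 190.
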